4.1.3 Demonstrate Usability

Validation of Claim 2 will justify Over-the-Counter (OTC) use of VR101.

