When the first ring is removed (Day 7, Visit 2/5 depending on study group), the participant will be asked to rate her level of agreement with the statement "the ring was easy to use by following the provided instructions" on a scale of -4 to 4 (see section 5.4.6). Claim 2 will be validated if the lower bound of the two-sided 95% confidence interval of the proportion of the study population that recorded favorable responses (participants recording a Score of 1, 2, 3 or 4) is greater than or equal to 0.80. The 95% confidence interval will be calculated using the exact test.

Claim 3: VR101 is comfortable during use.

In each daily diary, the participant will be asked to rate her level of agreement with the statement "the ring was comfortable to me today" on a scale of -4 to 4 (see section 5.4.6). Claim 3 will be validated if the lower bound of the 95% confidence interval of the proportion of the study population that recorded favorable responses (participants recording a Score of 1, 2, 3 or 4) is greater than or equal to 0.80. The 95% confidence interval will be calculated using the exact test.

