4. Participants will undergo a brief vaginal health assessment which will include a pH test and assignment of VHI scores (see Table 6). During Visit 1, if a participant is assigned a VHI score of 22 or lower (and met all other inclusion/exclusion criteria), she will be enrolled in the study and randomized. The participant will be assigned the next available (lowest remaining) Participant Number.
5. Enrolled participants will be provided with a package of either at least 6 each VR101 devices or at least 6 each sham controls (one for each of the first 4 weeks and at least 2 spares) with printed instructions for use. During Visit 1, the Participant will be given a package containing the Participant Number followed by the letter "A" (for example Participant 1 will be given a package labeled "1A"). During Visit 4, the Participant will be given a package containing the Participant Number followed by the letter "B" (for example Participant 1 will be given a package labeled "1B"). Participant numbers will be pre-randomized by the Sponsor, and only the Sponsor will have access to the randomization schedule. No additional information, verbal or otherwise, will be provided by the clinician to participants on the use of the device.
6. Enrolled participants will be shown to a private clinic area or restroom to self-insert one of the devices from package "A" (Visit 1) or "B" (Visit 4).
7. After insertion, participants will be asked to complete a Post-Insertion Survey that queries their first impressions of the IVR and the insertion process. If a participant has difficulty with placement, she can choose to not place the ring and will be withdrawn from the study. The first ring will remain in the vagina for 7 ± 2 days.
8. Participants will be given a daily diary to complete and return to study staff at each subsequent study visit. The diary will request information on comfort of device use during daily activities and symptoms of vaginal dryness.

J3 Bioscience, Inc.	Clinical Investigation Plan and Protocol CI02	CI02-CIP Rev. 08 Page 39 of 75
	A Pivotal Clinical Investigation to Evaluate the Safety and Efficacy of J3 Bioscience Lubricating Intravaginal Ring VR101 in Relieving Symptoms of Vaginal Dryness	

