5.4.6 Additional Participant Surveys (Exploratory Endpoints unless noted)

At each clinical visit and in daily diaries, participants will be given statements and asked to score their level of agreement or disagreement as follows:

"Disagree completely"	(assigned a score of -4)
"Disagree a lot"	(assigned a score of -3)
"Disagree somewhat"	(assigned a score of -2)
"Disagree a little"	(assigned a score of -1)
"Neither agree nor disagree"	(assigned a score of 0)
"Agree a little"	(assigned a score of 1)
"Agree somewhat"	(assigned a score of 2)
"Agree a lot"	(assigned a score of 3)
"Agree completely"	(assigned a score of 4)

The following statements will be presented as part of clinical visit surveys (see Section 5.4.3 for clinical visit schedule). Only statements pertinent to non-exploratory endpoints are detailed below. Each survey will contain additional statements and questions designed for exploratory evaluations of VR101 use. Refer to the survey Case Report Forms (Attached), for the complete set of survey questions.

J3 Bioscience, Inc.	Clinical Investigation Plan and Protocol CI02	CI02-CIP Rev. 08 Page 44 of 75
	A Pivotal Clinical Investigation to Evaluate the Safety and Efficacy of J3 Bioscience Lubricating Intravaginal Ring VR101 in Relieving Symptoms of Vaginal Dryness	

Post-Removal Survey

The ring was easy to use by following the provided instructions (Data from Visit 2 will be used to Assess Claim 2)

Daily Diary

The statement *“the ring was comfortable to me today”* will be included as part of a daily diary (used to assess the validity of Claim 3).

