8.12 Definition of Study Populations for Analysis

THE FOLLOWING STUDY POPULATIONS HAVE BEEN DEFINED FOR THIS INVESTIGATION:

Intent-to-Treat (ITT) Primary Efficacy Hypothesis Population: All patients who meet inclusion/exclusion criteria and are randomized will be included. Any missing day 0 or day 28 VHI scores will be imputed as defined in section 8.8.

J3 Bioscience, Inc.	Clinical Investigation Plan and Protocol CI02	CI02-CIP Rev. 08 Page 57 of 75
	A Pivotal Clinical Investigation to Evaluate the Safety and Efficacy of J3 Bioscience Lubricating Intravaginal Ring VR101 in Relieving Symptoms of Vaginal Dryness	

Menopausal Population: All members of the ITT population who self-report to being menopausal (have not experienced a menstrual period in the 12-month period prior to the study).

Safety Population: All VR101 devices in all study arms that are successfully inserted and used in accordance with the provided instructions for use will be included as a basis for determination of SADE proportion.

Claim 1 Population: All participants who report a daily vaginal dryness severity following their first VR101 use (Visit 2/5, depending on study arm) and report a weekly average vaginal dryness severity prior to their first VR101 insertion (Visit 1/4, depending on study arm), will be included in the analysis for Claim 1. See section 5.4.5 for relevant survey questions.

Claim 2 Population: All participants in group V1S2 who respond to the appropriate survey question (see section 5.4.6) immediately following their first VR101 insertion (Visit 1) will be included in the analysis for Claim 2.

Claim 3 Population: All daily diary responses recorded regarding VR101 comfort during use (see section 5.4.6) will be included in the analysis for Claim 3.

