21.2 Appendix B – Participant Survey Questions Used for Validation of Claims

Claim 1: VR101 relieves vaginal dryness symptoms for up to 7 days in a majority of participants, as assessed by users.

The following question will be asked during Visit 1 and 4. The responses recorded immediately prior to insertion of the first VR101 will be used as the baseline value for validation of claim 1.

On AVERAGE, how would you rate your VAGINAL DRYNESS over the **Past 7 Days**? That would be since the last (day of the week)

I have not experienced vaginal dryness **Mild** **Moderate** **Severe**

The following definitions are also given prior to asking the question:

- When we say "**mild**," we mean that any symptoms you have cause **NO or MINIMAL interference** with your usual social or functional activities.
- When we say "**moderate**," we mean that your symptoms cause **MORE THAN MINIMAL interference** with usual social and functional activities.
- When we say "**severe**," we mean that your symptoms cause an **INABILITY** to perform some or all of your usual social and functional activities.

The following question will be asked at each visit. The responses recorded immediately following use of the first VR101 device (Visit 2 or Visit 5) will be used to assess the validity of claim 1.

Rate your vaginal dryness TODAY, that is, in the last 24 hours?

I have not experienced vaginal dryness *Mild* *Moderate* *Severe*

The following definitions are also given prior to asking the question:

- When we say "**mild**," we mean that any symptoms you have cause **NO or MINIMAL interference** with your usual social or functional activities.
- When we say "**moderate**," we mean that your symptoms cause **MORE THAN MINIMAL interference** with usual social and functional activities.
- When we say "**severe**," we mean that your symptoms cause an **INABILITY to perform some or all** of your usual social and functional activities.

J3 Bioscience, Inc.	Clinical Investigation Plan and Protocol CI02	CI02-CIP Rev. 08 Page 75 of 75
	A Pivotal Clinical Investigation to Evaluate the Safety and Efficacy of J3 Bioscience Lubricating Intravaginal Ring VR101 in Relieving Symptoms of Vaginal Dryness	

Claim 2: VR101 is easy to use by following the provided instructions for use.

The following question will be asked as part of each post-removal questionnaire. Responses recorded following removal of the first VR101 will be used to assess the validity of Claim 2.

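### Claim 2, the stated basis for OTC use, has conflicting analysis sets; one cannot be applied as written, one adds practised users, and none counts women who could not place the ring

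*Combined protocol and SAP*

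**What the plan says.** Section 4.1.3 states what the claim is for: "Validation of Claim 2 will justify Over-the-Counter (OTC) use of VR101". Section 4.2.3 sets the test: the exact two-sided 95% lower bound on the favourable proportion must be at least 0.80. The data that enter the test are described in four places.

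- **Section 4.2.3:** "When the first ring is removed (Day 7, Visit 2/5 depending on study group), the participant will be asked" to rate ease of use. This takes both groups, each at removal of its first VR101.
- **Appendix B (21.2):** "Responses recorded following removal of the first VR101 will be used to assess the validity of Claim 2". No group restriction. On where the item sits: "The following question will be asked as part of each post-removal questionnaire".
- **Section 5.4.6:** under the Post-Removal Survey, "Data from Visit 2 will be used to Assess Claim 2". No group is named.
- **Section 8.12:** "All participants in group V1S2 who respond to the appropriate survey question (see section 5.4.6) immediately following their first VR101 insertion (Visit 1"). V1S2 only, after insertion.

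On women who cannot insert the ring, Section 5.4.3 (Visit 1/4, step 7) says: "If a participant has difficulty with placement, she can choose to not place the ring and will be withdrawn from the study".

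**The concern.** Section 3.7 says an OTC user must manage insertion and removal from the instructions and labelling alone. The relevant evidence is therefore first use by women new to the ring, including those who fail. The plan departs from that in two ways, and both favour the claim.

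First, if Section 4.2.3 and Appendix B govern, about half the answers come from S1V2 women at Visit 5. They have by then used four sham rings (5.1) that look very similar (5.1.2) and carry identical instructions and labels (5.6). Any S1V2 woman who could not place a sham has already gone.

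Second, the item reaches only women who placed a ring and answered. A woman who could not place it is the clearest counter-example to the claim, yet no rule gives her a Claim 2 score.

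With several definitions on the page, the choice among them could also be made after the results are seen.

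**Working it through.** **Which definitions can be applied.** The list of case report forms gives the Post-Removal Survey at Visits 2-3 and 5-9, and Table 4 agrees. Visit 1 has the Pre-Study and Post-Insertion surveys. The item in Appendix B asks about the whole experience from last week's insertion to today's removal, so it has no meaning minutes after a first insertion. Section 8.12 taken literally therefore selects answers that are not collected. Changing its visit to first removal at Visit 2 makes it workable, but V1S2 alone still conflicts with both groups in 4.2.3 and Appendix B. The restriction looks deliberate: the Claim 1 population in the same section names Visit 2/5 by arm, while Claim 2 names V1S2 only.

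**The plan's own figures.** No sample size, expected rate or power is stated for Claim 2. The number of women comes from primary efficacy (8.2): n = 60, difference 0.89, SD 2.14, two-sided 0.05, stated power 88%. Noncentral t with noncentrality 0.89/2.14 × √60 = 3.22 gives 88.7%, so that figure reproduces. It says nothing about Claim 2.

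**Inputs for Claim 2.**
- 72 enrolled (5.3.6). The allocation ratio is not stated; 1:1 is assumed, giving 36 in V1S2.
- 11 of 72 withdrew in the crossover, reasons not given (8.4); 72 − 11 = 61.
- Placement failures and any practice effect: not in the documents. All counts below are assumed.

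**Formula.** The exact lower bound for x favourable out of n is the 2.5% quantile of Beta(x, n − x + 1). Pass if it is at least 0.80.

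**Leaving out women who could not place the ring.**

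| Favourable / n | Lower bound | Result |
|---|---|---|
| 33/34 (two failures left out) | 0.847 | pass |
| 33/35 (one failure counted) | 0.808 | pass |
| 33/36 (two failures counted) | 0.775 | fail |
| 34/36 (fewest that pass at n = 36) | 0.813 | pass |
| 34/37 (34/36 plus one failure) | 0.781 | fail |

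One failure reverses a result that only just passes, but does not reverse 33/34.

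**Adding practised users.** Assume 30 per group, with 26/30 favourable in V1S2 and 29/30 in S1V2. V1S2 alone: lower bound 0.693, fail. Pooled: 26 + 29 = 55 of 60, lower bound 0.816, pass. With assumed true rates of 0.85 (first use) and 0.95 (practised), the chance of passing is 4.8% on V1S2 alone (29/30 needed) and 43% pooled (55/60 needed).

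**Price of the smaller set.** The chance of passing is P(X ≥ r) for X binomial(n, p), where r is the fewest favourable answers that pass.

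| n | r | p = 0.90 | p = 0.95 |
|---|---|---|---|
| 36 | 34 | 29% | 73% |
| 61 | 56 | 42% | 92% |

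**The case against.** The best defence is that the plan, read as a whole, already means V1S2 women at Visit 2. Section 8.12 points to the question in 5.4.6, which is the Post-Removal item at Visit 2, so the mention of insertion at Visit 1 is probably a slip. That is fair. A reader might infer that Claim 2 would have no data at all, and the documents do not support this: the item is collected at Visit 2 and Visit 5. The full case report forms are also not reproduced, although 5.4.6 sets out the statements for non-exploratory endpoints and lists this one only under Post-Removal. What survives is the conflict over groups with 4.2.3 and Appendix B.

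A reader might also infer from 5.4.6 that S1V2 ratings of the sham at Visit 2 could count. That is strained. Endpoint 3 (5.1.1) is ease of use of VR101, and Appendix B specifies the first VR101. Section 5.4.6 only needs to name the group.

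On size, no placement failure in this trial is documented. Pilot participants all managed insertion and removal unaided (3.7), and a history of inability to place a vaginal ring is an exclusion (5.3.2). With 21 pilot women a low failure rate is not ruled out, but none is shown. The figure of 61 is those left after the full crossover; women who answered before withdrawing would still count, so the 4.2.3 set could be larger.

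Section 4.2.3 does speak of a proportion of the study population, which might be read as a full denominator. No text puts that into effect.

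**Conclusion.** The concern holds. The Claim 2 definitions contradict one another, 8.12 cannot be followed literally, and no version scores a woman who could not place the ring. Leaving her out can only raise the favourable proportion. Including S1V2 at Visit 5 measures experienced rather than first use, which would favour the claim if practice helps.

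The size is unknown. The reversals shown (33/34 against 33/36; 26/30 against 55/60) rest on assumed counts, 1:1 allocation in the first case and 30 women per group in the second. They show that one or two women, or the choice of group, can decide the result. A reader might infer that the claim will pass wrongly or that women were lost for placement difficulty; the documents support neither, since the 11 withdrawals carry no reasons.

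The consequence is bounded. Claim 2 has no effect on overall study success (8.5), but it gates Claim 3 (8.11) and is the stated ground for OTC use.

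**What to change.** Before the crossover blind is broken (Section 9), put one definition into 4.2.3, 5.4.6, 8.12 and Appendix B:

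- **Data:** the Visit 2 Post-Removal item in women randomised to V1S2. Section 5.4.6 should name V1S2.
- **Denominator:** every V1S2 woman who attempted her first VR101.
- **Scoring:** women documented as unable to place it, or as stopping before Visit 2 because of insertion or removal difficulty, count as not favourable. Where the reason was not recorded, show the result with the woman counted as not favourable and with her left out.
- **S1V2 at Visit 5:** report separately as experienced use.

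The change is wording in four places and uses an item already collected. It does need reasons for stopping. Appendix A has monitors verify that withdrawals are documented, but the text describes no field for the reason, hence the two-way display. The main cost is the smaller set: 34 of about 36 must be favourable, and the chance of passing falls from about 92% to about 73% at a true rate of 0.95, and from 42% to 29% at 0.90. Revision 08 already reports crossover withdrawals, so many answers may be in hand. The amendment should record that the rule was fixed without sight of unblinded data.

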5.2 Investigational and Predicate Devices

5.2.1 Exposure to VR101 and the sham control

Participants will use VR101 for up to 17 weeks total and the sham control for 4 weeks as described above. Participants will use VR101 for approximately 13 total weeks, consecutively, to evaluate device safety.

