5.3.4 Duration of Participation

Participants will be enrolled in the study for up to 25 weeks. This will consist of a crossover study, (4 weeks of VR101/sham use, 3-week washout period, 4 weeks of sham/VR101 use), then up to 13 additional weeks VR101 use in the open-label, long-term safety evaluation, followed by a follow-up questionnaire completed 1 week after the last VR101 device is removed.

Participants will be randomly assigned to either Group S1V2 or Group V1S2. Participants in Group S1V2 will complete the crossover study (11 weeks: 4 weeks sham followed by 3 weeks wash-out followed by 4 weeks VR101) and will continue to the long-term safety evaluation (10 additional weeks, including the final follow-up call). Participants in Group V1S2 will complete the crossover study (11 weeks: 4 weeks VR101 followed by 3 weeks wash-out followed by 4 weeks sham), and will participate in the long-term safety study (13 additional weeks of VR101 use plus a final follow-up call conducted 1 week after removal of the last VR101 device [14 weeks total]).

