5.3.6 Number of Participants

72 participants (36 at each study site) were enrolled in CI02 with a goal of at least 60 completing the efficacy evaluation (first 11 weeks and 6 study visits) and at least 30 completing the long-term safety evaluation. Based on our drop-out rate analysis (see Section 8.4), we calculate that continuation of at least 42 participants to the long-term safety evaluation will ensure that 30 will complete the entire study. All participants will be automatically selected to participate in the long-term safety portion of the investigation.

To ensure that 60 participants successfully complete the study (and that 30 participants successfully complete the long-term safety study), it will still be possible to enroll participants to replace drop-outs at any point during the study until 60/30 participants have successfully completed the study, provided that the crossover study blind has not yet been broken (although active recruitment may discontinue when the estimated enrollment is met as described above). Note that if additional sites are used, the requirement for the minimum number of patients at each site will be modified accordingly.

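### Claim 3 (comfort): section 4.2.3 tests a proportion of women, section 8.12 analyses every diary response, and neither gives a per-woman rule or allows for repeated ratings

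*Combined protocol and SAP*

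**What the plan says.** Section 4.2.3 sets the rule for comfort: "Claim 3 will be validated if the lower bound of the 95% confidence interval of the proportion of the study population that recorded favorable responses" is at least 0.80. In parentheses it defines the favourable group as "participants recording a Score of 1, 2, 3 or 4", and it adds: "The 95% confidence interval will be calculated using the exact test". The rating is made in each daily diary, so a woman who uses four rings for seven days gives about 28 VR101 ratings in the crossover alone.

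Section 8.12 defines the Claim 3 population differently: "All daily diary responses recorded regarding VR101 comfort during use (see section 5.4.6) will be included in the analysis for Claim 3". The same list defines Claims 1 and 2 by participants. Section 8.1 also describes these proportions in terms of favourable survey responses.

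Two further details bear on the test.

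- **Sidedness.** For ease of use, 4.2.3 writes "Claim 2 will be validated if the lower bound of the two-sided 95% confidence interval"; the comfort rule omits the word two-sided.
- **Period.** 8.12 sets no time limit. Section 5.2.1 says "Participants will use VR101 for up to 17 weeks total", and section 5.3.4 describes the crossover, "then up to 13 additional weeks VR101 use in the open-label, long-term safety evaluation".

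Sections 4.2.3, 5.1.1, 5.4.6, 8.1, 8.8, 8.9, 8.12 and Appendix B contain neither a rule for turning a woman's ratings into one outcome nor a method for repeated ratings.

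**The concern.** The unit differs between the hypothesis and the analysis set, and neither version can be run validly as written. With the response as the unit, an exact binomial interval assumes independent ratings. Daily ratings of the same device by the same woman are likely to be correlated, and a positive correlation makes the interval too narrow. With the woman as the unit, 28 or more ratings must become one yes or no, and the plan does not say how.

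At stake is the comfort labeling claim. It could be called validated with a true error well above what a 95% interval implies, or its verdict could rest on a choice the analyst makes after seeing the data.

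**Working it through.** The plan gives no sample size, power or expected rate for Claim 3, so there is no figure of its own to reproduce.

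**Inputs from the documents**
- Women: 60, from section 5.3.6 ("with a goal of at least 60 completing the efficacy evaluation").
- Crossover VR101 diary days per woman: 4 rings x 7 days = 28, so 60 x 28 = 1,680 responses.
- Bound: exact 95% lower limit of at least 0.80 (4.2.3).

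**Assumptions**
- The interval is two-sided (Claim 3 does not say), every woman has the same number of diary days, and the true proportion of favourable days is 0.80.
- The ICC is not in the documents and is varied.

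**Pooled pass mark.** The Clopper-Pearson lower limit is the 0.025 quantile of Beta(x, n - x + 1). With n = 1,680, x = 1,377 gives 0.8004 and x = 1,376 gives 0.7998. Pooling therefore passes at 1,377/1,680 = 82.0%.

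**False validation under pooling.** Each woman's favourable count is beta-binomial with m = 28, a = 0.8(1 - ICC)/ICC and b = 0.2(1 - ICC)/ICC. The exact distribution of the sum over 60 women gives:

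| ICC | P(pass) at a true 80% of days |
|---|---|
| 0 | 2.3% |
| 0.0016 | 2.5% |
| 0.01 | 3.8% |
| 0.05 | 9.6% |
| 0.1 | 15.1% |
| 0.3 | 26.1% |
| 0.5 | 31.0% |

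*Hand check at ICC 0.1.* The design effect is 1 + 27 x 0.1 = 3.7. The standard error is sqrt(0.8 x 0.2 x 3.7 / 1,680) = 0.0188. With a continuity correction, (1,376.5/1,680 - 0.80)/0.0188 is about 1.03, an upper tail of about 15%.

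**If the interval is one-sided 95%.** The pass mark is 1,372. The error is 4.6% under independence, 19.3% at ICC 0.1 and 29.6% at ICC 0.3.

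**If long-term diaries count.** The days are 13 x 7 = 91 for S1V2 and up to 17 x 7 = 119 for V1S2.
- With 30 women per group all completing, n = 30 x 91 + 30 x 119 = 6,300 and the pass mark is 5,103. The error is 28.6% at ICC 0.1 and 37.5% at ICC 0.3.
- With only 30 completing, n = 15 x 91 + 15 x 119 + 30 x 28 = 3,990 and the pass mark is 3,242. The error is 27.2% and 36.8%.

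**If the woman is the unit.** The exact test needs 55/60 women. Who counts as favourable depends on the missing rule. Take a true 85% of favourable days and ICC 0.1:
- More than half of days (at least 15 of 28): 97.8% of women count, and 55/60 is reached with probability 0.998.
- All 28 days: 12.8% of women count, and 55/60 is practically out of reach.

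**The case against.** The strongest reply is that 4.2.3 states the test at participant level twice, so 8.12 may only name where the data come from. On that reading there is no inflated error. This stands as a limit: every inflated rate above is conditional on pooling and on an assumed ICC, and the documents do not say outright that responses are pooled as independent. It does not remove the problem, because 4.2.3 then lacks the outcome it needs.

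Three stronger readings are tempting but not supported.

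- A reader might set 85% of diary days beside 85% of women and conclude that the two units give opposite verdicts on the same data. A share of days is not a share of women. Under the more-than-half rule above, the per-woman verdict would almost always agree with pooling.
- A reader might infer that one outcome per woman restores the error rate for the same hypothesis. It controls error for a proportion of women. At a true 80% of days and ICC 0.1, the more-than-half rule passes with probability 0.93.
- A reader might infer from Tables 4 and 5 that diaries are not collected after Visit 6. The columns are shifted in the extracted text, and sections 5.4.3 and 5.4.7 have diaries returned at each subsequent visit. What can be said is that the period for Claim 3 is not stated explicitly.

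The 6,300-response case is an upper bound: sections 5.3.5 and 5.4.3 have V1S2 women asked to stop VR101 when the blind is broken.

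The consequence is also limited. Section 8.5 says the claims do not affect trial success, and under 8.11 comfort is tested only after efficacy, safety, Claim 1 and Claim 2 have passed.

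**Conclusion.** The concern holds as a conflict of unit plus a missing method. Applied to the set defined in 8.12, the exact interval is too narrow for all but negligible within-woman correlation. The error passes 2.5% at an ICC of about 0.0016 and is 15.1% at 0.1 and 26.1% at 0.3, for 60 women x 28 days and a two-sided interval. It is higher if long-term diaries or a one-sided interval are used. Read at participant level, the test cannot be run until a per-woman rule is written. This should be corrected for the sake of the labeling claim; it does not threaten the trial's primary conclusions.

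A separate drafting conflict affects Claim 2. Section 8.12 takes V1S2 women responding just after insertion at Visit 1. The item is on the Post-Removal Survey, first given at Visit 2, and 4.2.3 uses Visit 2 or 5 in both groups. Section 4.1.3 rests OTC use on this claim, and Claim 2 gates Claim 3.

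**What to change.** Before the blind is broken:

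1. Keep the 0.80 bound and make 4.2.3 and 8.12 state the same unit.
2. Use a two-sided 95% interval that accounts for clustering by woman. One option: take each woman's proportion of favourable VR101 diary days, average with equal weight per woman, and form a t interval on the logit scale with participants minus 1 degrees of freedom. If every response is favourable, use the exact per-participant bound (0.025^(1/60) = 0.940 for 60 women). In simulation with 60 x 28, this interval's error at a true 80% was about 2.4% to 2.7% for ICC 0.01 to 0.5. Other cluster-adjusted intervals would also serve.
3. Alternatively, define one outcome per woman in advance and keep the exact test, stating that it tests a different quantity.
4. State which diary period counts, and whether open-label diaries are included.
5. For Claim 2, correct 8.12 to the Post-Removal response after the first VR101 ring, and make the group the same in 4.2.3, 5.4.6, 8.12 and Appendix B. Whether that is V1S2 alone or both groups is for the sponsor to decide and record.

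**Cost.** No new data are needed: this is wording and a short program change, with the Sponsor and IRB approval that section 10 requires. The interval is wider, so the chance of validating Claim 3 falls. At a true 85% of days it is 76%, 38% and 25% at ICC 0.1, 0.3 and 0.5, against 96%, 88% and 82% with pooling, whose error is not controlled. At a true 90% it is 100%, 94% and 79%.
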